7.1 ELIGIBILITY ASSESSMENT

Subjects are considered eligible for this study if they meet all of the inclusion criteria and none of the exclusion criteria as defined in **Section 6.1** and **Section 6.2**. The Investigator, co-Investigator, or sub-Investigator performing the study surgery will confirm eligibility.

7.2 ENROLLMENT

Enrollment in the study occurs upon clinical confirmation that the subject meets all of the inclusion criteria and none of the exclusion criteria. Patients who do not meet study eligibility criteria at the time of the study procedure will undergo tendon repair at the discretion of the surgeon (without use of the Rotation Medical Bioinductive Implant) and will not be enrolled in the study. The date of the study surgery is defined as the enrollment date and all subjects who are enrolled in the study will be followed per protocol unless voluntary consent is withdrawn. All subjects enrolled into the study will be identified through a unique identifier.

7.3 BASELINE ASSESSMENT

During the baseline assessment, the following activities must be conducted within 60 calendar days prior to enrollment:

1. Obtain written informed consent

²Each study MRI must be performed in accordance with the MRI study guideline.

³Only prescription medications to treat the index Achilles will be recorded.

⁴Non-serious AEs will only be recorded if they are classified as either possibly or definitely related to either the study device or the study procedure.

⁵Any additional surgical intervention performed on the index Achilles will be reported.

- 2. Obtain medical history
- 3. Perform an MRI per the Sponsor imaging guidelines
 - Provide the Sponsor with a de-identified digital copy, or access to the MRI
- 4. Assess subject eligibility based on inclusion/exclusion criteria defined in **Section 6.1** and 6.2.
- 5. Record prescription medications
 - Record any prescription medications the subject is taking at the time of the baseline visit to treat his/her index Achilles
- 6. Administer VISA-A (Victorian Institute of Sports Assessment-Achilles questionnaire) form to assess Achilles tendon pain.

7.4 PROCEDURE ASSESSMENT

During the study procedure, use of any biological agents or implants aimed at augmenting tendon-to-bone healing, excluding the Rotation Medical Bioinductive Implant, are strictly prohibited. Intra-operative data along with the following study-specific procedure information will be documented on the Procedure CRF:

- 1. Device implant time
- 2. Procedure technical success
- 3. Device implant position
 - After implantation of the device, an intra-operative photograph(s) or video recording showing the implant location of the device and all tendon and bone staples will be obtained.
- 4. Intra-operative complication (if applicable; per Section 8)

7.5 PROCEDURE RULES

Subjects should be scheduled to undergo the study procedure within 60 days of baseline assessment. Device implantation will be performed in accordance with the Rotation Medical Bioinductive Implant System device and instrument Instructions for Use (IFUs) and may be performed as an open procedure.

All subjects will be place in a supine position with a small bump under the contralateral hip. A tourniquet will be placed on the operative leg. A standard incision will be placed just medial to the Achilles tendon. The Achilles will be detached from the calcaneus, undergo debridement and assessed for integrity. The posterior aspect of the calcaneus will undergo exostectomy. At the surgeon's discretion the flexor hallucis longus tendon will be harvested. The Achilles tendon will be re-attached to the posterior aspect of the calcaneus using suture anchors. If the FHL is harvested a supplemental oblique tunnel will be created using a small burr. The FHL will be passed through the tunnel, woven through and attached to the remaining debrided Achilles tendon. Following the bioinductive implant will be attached to the Achilles tendon.

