4.3 PRIMARY OUTCOME MEASURES

4.3.1 Increase in Tendon Thickness

Achilles tendon thickness will be measured pre-operatively (baseline) and the total thickness of the tendon and any newly induced tissue at the implant site will be measured at each follow-up visit using magnetic resonance imaging (MRI). The mean (\pm SD) change in post-operative Achilles tendon thickness will be calculated at each follow-up interval.

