4.3.2 Integration and Maturation of New Tissue

Integration and maturation of the newly induced tissue will be assessed by MRI at each post-operative follow-up. This outcome will assess, at a minimum, the following characteristics of the newly induced tissue: (i) presence or absence of a clear boundary between the device and the underlying tendon; (ii) maturation of newly induced tissue to resemble characteristics of underlying tendon tissue (versus debris, artifact, or calcification).

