5 STATISTICAL ANALYSIS PLAN

This is an initial feasibility study and not powered to address the hypotheses. Changes in tendon thickness over the time of the follow up visits will be assessed by a Repeated Measures ONEWAY ANOVA with a post hoc Scheffe. Indices of new tissue integration and maturation at each follow up visit will be assessed by Chi Square analyses.

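### Unless the MRI guideline separates the tissues, pooled change in total tendon thickness from the pre-operative MRI cannot be attributed to bioinduction alone

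*Combined protocol and SAP*

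**What the plan says.** The objective (Section 3) has two parts: induction of new tissue and tendon healing. Increase in tendon thickness is the first primary outcome. Under Section 4.3.1 the reference value comes from the MRI before surgery. After surgery, "the total thickness of the tendon and any newly induced tissue at the implant site will be measured at each follow-up visit". The summary is a single mean (SD) per visit: the "change in post-operative Achilles tendon thickness will be calculated at each follow-up interval".

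Section 7.5 describes what happens between those scans. For every subject, "The Achilles will be detached from the calcaneus, undergo debridement and assessed for integrity". If the surgeon so decides, the "flexor hallucis longus tendon will be harvested", passed through a bone tunnel, and then "woven through and attached to the remaining debrided Achilles tendon". The implant is attached last. Section 1 describes FHL augmentation as often needed in this operation but gives no rate for this study.

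The study has one arm (Section 4), and the first post-operative MRI is at 3 months (Table 7-1). Section 5 says: "Changes in tendon thickness over the time of the follow up visits will be assessed by a Repeated Measures ONEWAY ANOVA". It names no FHL factor, subgroup or listing. Section 7.4 puts intra-operative data and four named items on the Procedure CRF; neither FHL use nor extent of debridement is among the four.

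Other MRI outcomes look at the tissue more directly. Section 4.3.2 assesses the "presence or absence of a clear boundary between the device and the underlying tendon" and the maturation of the new tissue. The synopsis also lists the amount of defect fill-in, which Section 4.3 does not carry forward.

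**The concern.** The two scans straddle an operation that changes thickness by itself. Debridement removes tissue in everyone, and an FHL weave may add tissue in some. The implant's contribution is read as part of a total that also contains both, with no comparator arm and no early post-operative scan to subtract them.

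An increase in the pooled mean could therefore be partly transferred tendon, and a null or negative mean could hide real induction behind tissue the surgeon removed. The study plans no powered test and sets no thickness criterion for success, so the descriptive mean is what readers will look to on thickness. For the bioinduction half of the objective they could misread it in either direction.

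**Working it through.** **Nothing to reproduce.** The plan gives no expected change, SD, alpha or sample-size calculation. From the documents come n (up to 10), the visit schedule and one effect size: about 2.5 mm in sheep (Section 1). Every other input below is an assumption.

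**Step 1: what the change contains.** For one subject at visit t, with I = induced tissue, R = tissue debrided and F = FHL tissue at the measured site (F = 0 without FHL):

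change(t) = I(t) - R + F

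One observed number has up to three unknown parts.

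**Step 2: zero induction, equal debridement.** Set I = 0 and n = 10. Assume k = 2 or 5 subjects receive FHL, FHL adds d = 1, 2 or 3 mm, and debridement removes r = 0.5, 1 or 2 mm in all. Pooled mean = (k/10)d - r, in mm:

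| k, d | r = 0.5 | r = 1 | r = 2 |
|---|---|---|---|
| 2, 1 | -0.3 | -0.8 | -1.8 |
| 2, 2 | -0.1 | -0.6 | -1.6 |
| 2, 3 | +0.1 | -0.4 | -1.4 |
| 5, 1 | 0 | -0.5 | -1.5 |
| 5, 2 | +0.5 | 0 | -1.0 |
| 5, 3 | +1.0 | +0.5 | -0.5 |

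Range -1.8 to +1.0 mm; of 18 settings, 12 are negative, 2 zero and 4 positive.

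**Step 3: zero induction, debridement at least as heavy in FHL cases.** FHL use follows the state of the tendon, so FHL cases may lose more tissue. Assume rF = 1 or 2 mm with FHL and rN = 0.5 or 1 mm without. Pooled mean = (k/10)(d - rF) - (1 - k/10)rN, in mm. Columns give d, rF:

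| k, rN | 1, 1 | 1, 2 | 2, 1 | 2, 2 | 3, 1 | 3, 2 |
|---|---|---|---|---|---|---|
| 2, 0.5 | -0.4 | -0.6 | -0.2 | -0.4 | 0 | -0.2 |
| 2, 1 | -0.8 | -1.0 | -0.6 | -0.8 | -0.4 | -0.6 |
| 5, 0.5 | -0.25 | -0.75 | +0.25 | -0.25 | +0.75 | +0.25 |
| 5, 1 | -0.5 | -1.0 | 0 | -0.5 | +0.5 | 0 |

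Range -1.0 to +0.75 mm; of 24 settings, 17 are negative, 3 zero and 4 positive.

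**Step 4: scale.** If true induction were the sheep figure of 2.5 mm, the same offsets would give 2.5 - 1.8 = 0.7 to 2.5 + 1.0 = 3.5 mm (Step 2), or 2.5 - 1.0 = 1.5 to 2.5 + 0.75 = 3.25 mm (Step 3). On these inputs an effect that large would keep its sign but not its size. A small or absent effect could show either sign.

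**Step 5: what splitting by FHL status achieves.** Without FHL, change = I - R. At I = 0 that is -0.5 to -2.0 mm on the Step 2 inputs, so debridement remains. A test between the groups would be of little use. The 95% half-width for the difference, with 8 degrees of freedom (t = 2.306), is 2.306 × sqrt(1/5 + 1/5) = 1.46 SD for 5 against 5, and 2.306 × sqrt(1/2 + 1/8) = 1.82 SD for 2 against 8.

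**Step 6: the ANOVA.** If only the 3-month, 1-year and 2-year visits enter, a stable offset (-R + F) adds the same constant to all three values of a subject. It moves the subject mean and leaves the within-subject deviations unchanged, so the time and residual sums of squares and F do not change. A numerical check gave F = 0.265, p = 0.770 both with and without a random offset per subject (SD 3 mm).

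**The case against.** The strongest reply is that the MRI guideline, which governs every study scan (Table 7-1, footnote 2), may already define the measured site or separate the tissues. Section 4.3.1 restricts measurement to the implant site, and Section 7.5 does not say that the weave overlaps it. FHL use is discretionary, so there may be no FHL cases at all. This stands, and it is why the point is conditional. It bears most on the FHL term. Debridement is universal, though its depth at the measured site is not stated either.

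Second, other MRI outcomes address the new tissue. That is partly right. Integration and maturation look at it directly, but Section 4.3.2 specifies no thickness for it. Defect fill-in in the synopsis is expressed as an amount and is relevant to refill after debridement, but Section 4.3 gives it no definition. No bias is claimed in those outcomes.

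Third, an uncontrolled feasibility study of an adjunct to repair cannot fully separate implant from operation. That also stands, and it limits both the importance of the point and what a fix can achieve.

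A reader might go further and infer that the Section 5 ANOVA has a distorted error rate. The documents do not support this. Section 5 speaks of change across the follow-up visits, and on that reading a stable offset cancels (Step 6). Only if baseline were a level would the time effect absorb the surgical change. Section 5 does not say that it is, and any rejection rate would rest on an assumed noise SD.

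**Conclusion.** The point holds in conditional form. As written, and unless the MRI guideline separates the tissues or the weave lies outside the measured site, the first primary outcome mixes induced, debrided and possibly FHL tissue. Neither its size nor its sign can be attributed to bioinduction alone.

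The magnitude cannot be derived from the documents. The ranges of -1.8 to +1.0 mm and -1.0 to +0.75 mm at zero induction rest entirely on the assumed FHL count, FHL thickness and debridement depth. They show only that the sign is not determined.

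Two further readings would go too far. One is that the pooled change has been shown to be contaminated by FHL; the plan permits that but does not establish it. The other is that the thickness outcome is uninformative; total thickness still bears on healing, the other half of the objective.

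This is a cheap improvement of minor importance: the study is unpowered, has at most 10 subjects and ties no success criterion to thickness.

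**What to change.** 1. Record FHL transfer (yes/no) and extent of debridement on the Procedure CRF, if the intra-operative data do not already capture them.
2. In Sections 4.3.1 and 5, add a descriptive listing of thickness change by subject and FHL status, without a test. Show integration and maturation, tear and (per the synopsis) defect fill-in results alongside. State that subjects without FHL are still affected by debridement.
3. Where the boundary assessed under Section 4.3.2 is visible, have the same reader record the induced layer's thickness separately on the scheduled MRIs. This mainly serves early scans, because the boundary is lost as the tissue integrates.
4. Limit the wording of conclusions on bioinduction accordingly.

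Change from the 3-month MRI could be an optional supplement: if R and F are stable, change(t) - change(3 months) = I(t) - I(3 months). It misses induction before 3 months. The evidence in Section 1 of induced tissue at that time comes from a shoulder study, and the text should say so.

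The cost is two CRF fields if absent, one listing, one extra reading per scheduled scan where the boundary is visible, and a few sentences. The drawback is very small and non-comparable groups: FHL use depends on tendon integrity, so a difference between them must not be read as an effect of FHL.

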7.6 POST-OPERATIVE CARE

Post-operative care, including discharge instructions, pain management, and frequency/duration of physical therapy/rehabilitation regimen are at the discretion of the surgeon. To minimize the likelihood that the integrity or position of the device is compromised after implant, recommended rehabilitation guidelines are provided in **Table 7.2.**

Table 7-2: Post-operative Rehabilitation Guidelines

Study Procedure	Rehabilitation Guidelines			
Device implant	Remain in post mold splint until follow up			
	Remain nonweight bearing on operative leg with crutches or walker			
	• Follow up in one week for evaluation and placement into CAM boot with heel lift			
	• Follow up at 2 weeks for suture removal			
	• Follow up at 4 weeks for partial heel lift removal and progression to neutral foot			
	Follow up at 4 weeks for start of physical therapy			
	• Fill out VISA-A (Victorian Institute of Sports Assessment-Achilles questionnaire) at 6 and 12 months			

7.7 FOLLOW-UP ASSESSMENTS

All subjects will undergo post-operative study assessments at 3 months, 1 year, and 2 years after discharge from the study procedure as described below and summarized in **Table 7.1**.

7.7.1 3-Month (± 15 Days) Follow-Up

- 1. Perform an MRI per the Sponsor Imaging guidelines.
 - Provide the Sponsor with a de-identified digital copy of, or access to, the MRI
- 2. Clinical Assessment
- 3. Record prescription medications
 - Record any prescription medications the subject is taking at the time of the follow-up visit to treat his/her index Achilles.
- 4. Record any new adverse events and update the status of any ongoing, previously-reported adverse events.
- 5. Report any new revision/additional Achilles surgeries performed on the index Achilles

7.7.2 1-Year (\pm 45 Days) Follow-Up

- 1. Perform an MRI per the Sponsor imaging guidelines.
 - Provide the Sponsor with a de-identified digital copy of, or access to, the MRI.
- 2. Clinical assessment
- 3. Administer the recovery/satisfaction questionnaire (VISA-A)
- 4. Record prescription medications.
 - Record any prescription medications the subject is taking at the time of the follow-up visit to treat his/her index Achilles.
- 5. Record any new adverse events and update the status of any ongoing, previously-reported adverse events.
- 6. Report any new revision/additional Achilles surgeries performed on the index Achilles.

7.7.3 2-Year (\pm 90 Days) Follow-Up

1. Perform an MRI per the Sponsor imaging guidelines.

- Provide the Sponsor with a de-identified digital copy of, or access to, the MRI.
- 2. Clinical assessment
- 3. Administer the recovery/satisfaction questionnaire.
- 4. Record prescription medications.
 - Record any prescription medications the subject is taking at the time of the follow-up visit to treat his/her index Achilles.
- 5. Record any new adverse events and update the status of any ongoing, previously-reported adverse events.
- 6. Report any new revision/additional Achilles surgeries performed on the index Achilles.

The results of all follow-up assessments will be documented on their respective CRFs. Each reportable adverse event (**Section 4.1.1**) will be documented on an Adverse Event CRF.

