4.4.3 Recovery

The following post-operative recovery parameters will be reported after discharge from the from study procedure:

- 1. CAM boot time: cumulative number of days spent in a CAM boot
- 2. Rehabilitation time: cumulative number of completed rehabilitation or physical therapy (PT) visits (mean \pm SD) to treat index Achilles
- 3. Return to work: cumulative number of days (mean \pm SD) between discharge and return to work (employed subjects only)
- 4. Return to normal daily activities (i.e. full, unrestricted activity): cumulative number of days (mean \pm SD) between discharge and return to normal daily activity

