4.4.4 Subject Satisfaction

Subject satisfaction is a self-reported measure of satisfaction with the outcome of the index surgery. The level of satisfaction is assessed with a 5-point Likert scale. Each subject will also be asked to indicate whether (s)he would recommend the study procedure to a friend ("yes/no").

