7 STUDY ASSESSEMENTS

The schedule of protocol-required study assessments is provided in **Table 7.1**. Adverse event (AE) reporting as required and defined in **Section 8** begins at the time of enrollment (i.e. intra-operative confirmation of eligibility) and concludes at the end of the study.

Table 7-1: Schedule of Study Assessments

	Baseline	Procedure	3-Month	1 Year	2 Year
Study Evaluation	Within 60 Days of Surgery	Within 60 Days of Baseline	± 15 days	± 45 days	± 90 days
Informed Consent	✓				
Medical History & Exam	✓				
Eligibility Assessment	✓	√ ¹			
Enrollment (Date of Surgery)		✓			
MRI	√ ²		✓2	✓2	√ ²
Procedure Data		✓			
Medications	✓3	✓3	✓3	✓3	✓3
Adverse Events		✓4	✓4	✓4	✓4
Recovery/Satisfaction			✓	✓	✓
Questionnaire					
Revision/Additional Achilles Surgery			√ 5	√ 5	√ 5

¹Eligibilty confirmation will be performed at the time of the study surgery to ensure the patient meets eligibility criteria. Patients who do not meet study eligibility criteria will not be enrolled in the study.

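### The 3-month visit list omits the recovery/satisfaction questionnaire that Table 7-1 requires, and the 1-year list labels it VISA-A; VISA-A and non-return also lack a reporting rule

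*Combined protocol and SAP*

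**What the plan says.** Section 7 presents Table 7-1 as binding: "The schedule of protocol-required study assessments is provided in" that table. Its recovery/satisfaction row is ticked at 3 months, 1 year and 2 years. It has no separate row for VISA-A.

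Section 7.7 states: "All subjects will undergo post-operative study assessments at 3 months, 1 year, and 2 years after discharge from the study procedure as described below", and adds that Table 7.1 summarises these assessments. The lists and the table should therefore match. The three lists differ:

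- 7.7.1 (3 months) has five items: MRI, clinical assessment, medications, adverse events and further surgery. It has no questionnaire.
- 7.7.2 (1 year) has "Administer the recovery/satisfaction questionnaire (VISA-A", with the bracket closed after the instrument name.
- 7.7.3 (2 years) has "Administer the recovery/satisfaction questionnaire", with no instrument named.

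On what the questionnaire contains, Section 4.4.4 says: "The level of satisfaction is assessed with a 5-point Likert scale", plus a yes/no item on recommending the procedure. Section 7.3 gives VISA-A a different job at baseline: "Administer VISA-A (Victorian Institute of Sports Assessment-Achilles questionnaire) form to assess Achilles tendon pain". Section 13.1 names a Recovery/Satisfaction form in its own right.

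Section 5 covers tendon thickness and tissue indices only; its last sentence is "Indices of new tissue integration and maturation at each follow up visit will be assessed by Chi Square analyses". Section 4.4.3 plans a mean and SD of days to return to work, "between discharge and return to work (employed subjects only", and of days to return to normal activity. It does not mention subjects who have not returned.

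**The concern.** Sections 4.4.3 and 4.4.4 give no visit times for recovery and satisfaction. The timing of these declared secondary outcomes rests entirely on Table 7-1 and the 7.7 lists, and these disagree. Coordinators often work from the visit list. One who did so here would collect no satisfaction rating at 3 months, and a rating not taken then cannot be reconstructed. The recovery counts in 4.4.3 are cumulative and could be collected at a later visit, but with longer recall. At 1 year the label could lead a site to hand out VISA-A and believe the satisfaction item was done.

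VISA-A is collected at baseline and 1 year but appears in no outcome and no analysis, so its change could go unreported or be reported only if favourable. Days to return are undefined for a subject who has not returned, so a plain mean would in effect leave that subject out.

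**Working it through.** The plan states no figure on this point, so there is none to reproduce. The check compares the sections and adds simple counts.

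**1. Table against lists**

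| Visit | Table 7-1 | Section 7.7 list | Agreement |
|---|---|---|---|
| 3 months | required | not listed | no |
| 1 year | required | listed, labelled VISA-A | scheduling yes, instrument no |
| 2 years | required | listed | yes |

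The clinical assessment item in 7.7.1 cannot be assumed to include the questionnaire, because 7.7.2 and 7.7.3 list the two separately.

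**2. Scheduled administrations**, with the full 10 subjects of Section 4.1 and complete follow-up:

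- Table 7-1: 3 × 10 = 30.
- 7.7 lists, with the 1-year item read as the satisfaction form: 2 × 10 = 20.
- 7.7 lists, with the 1-year item read as VISA-A only: 1 × 10 = 10.

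These count schedule entries. They do not predict missing data.

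**3. Window for the first form**, taking 3 months as 90 days and using the Table 7-1 windows:

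- Table 7-1: 90 ± 15, days 75 to 105.
- 7.7 lists, 1-year item read as the satisfaction form: 365 ± 45, days 320 to 410.
- 7.7 lists, 1-year item read as VISA-A only: closes at 730 + 90 = day 820.

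**4. VISA-A.** It is collected at baseline (7.3) and 1 year (7.7.2). Table 7-2 also asks for it at 6 and 12 months, but there is no 6-month study visit. It is absent from 4.3, 4.4 and Section 5. The recovery/satisfaction row has no baseline tick, so baseline VISA-A is missing from Table 7-1 on any reading.

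**5. Return times.** Suppose k of n eligible subjects are followed to time T without returning, and the returners' mean is m. The mean of observed return times is m. Counting the others at T gives ((n − k)m + kT)/n, which is larger by k(T − m)/n whenever T exceeds m. True return times lie beyond T, so the plain mean understates recovery time in that case. For a subject who leaves early with status unknown, the direction is unknown. The documents give no k, m or number employed, so no size can be attached.

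**6. When a Kaplan-Meier median is reached.** A count of returners does not settle this under early censoring. Take n = 5. Two subjects exit before anyone returns, two of the remaining three return, and one does not. The curve falls to 2/3, then to 2/3 × 1/2 = 1/3. The median is reached although only 2 of 5 returned.

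**The case against.** The protocol has safeguards. Table 7-1 is the stated schedule, Section 10 makes a missed activity a deviation, and Sections 14.2 and 15 provide training and monitoring. A site following the table would collect the form at all three visits. This stands as mitigation, but training and monitoring need one consistent text to enforce.

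A reader might infer that table and list disagree about whether the questionnaire is due at 1 year. They do not: both schedule it, and only the instrument label conflicts. The label might also mean that the form includes VISA-A. The form itself is not in the documents, so replacement of the satisfaction items is a possibility only. Sections 4.4.4, 7.3 and 13.1 favour two separate instruments.

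A reader might also infer that the plan restricts the mean days to those who returned. It does not say so. Its only written restriction is employment, for return to work. The supported statement is that a rule is missing.

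Finally, this is a single-arm feasibility study of up to 10 subjects that Section 5 describes as unpowered, and a Kaplan-Meier estimate in so few subjects is imprecise. That is fair, and it is why the number returned and individual times should come first. It does not excuse an undefined summary.

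**Conclusion.** The contradiction is in the text. It is unambiguous at 3 months, where a required questionnaire is not listed. At 1 year it is confined to the instrument label. One of the three visits agrees fully. A site following 7.7.1 as written would lose 3-month satisfaction. The extent of any loss is unknown because it depends on which text sites follow.

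Two lesser points stand: VISA-A is collected without an outcome or summary, and 4.4.3 has no rule for non-return. The second understates recovery time only if someone is followed without returning, and the documents do not support an estimate of that effect in days.

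Severity is minor. Secondary or undeclared outcomes are affected; the primary MRI outcomes are not.

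**What to change.** 1. Add the recovery/satisfaction questionnaire to 7.7.1. List it and VISA-A as separate items in 7.7.2 and as separate rows in Table 7-1. State in 7.7.3 whether VISA-A is due at 2 years. Reconcile the 6-month VISA-A entry in Table 7-2 with the visit schedule.
2. Report the paired change in VISA-A from baseline to 1 year descriptively: mean change, 95% confidence interval and number of pairs, with no test. Label it secondary or exploratory.
3. In 4.4.3, report the number returned out of those eligible (employed subjects for work) and list individual times. Add a Kaplan-Meier median with non-returners censored at last contact. Write that the median is not reached only if the estimated curve does not fall to 50% or below.
4. Clerical: correct Section 13.1, which names two shoulder surveys as source data and does not name VISA-A.

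The cost is a short amendment under Section 14.6, with matching form and training wording. No new visit is needed for the questionnaire or the summaries; the 6-month VISA-A entry needs a decision on where it belongs. If there are non-returners, the reported recovery time may look less favourable.
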